Appendix 4 KTX-101 Normal Ranges for Vital Signs and ECG Parameters**VITAL SIGNS**

Parameter	Normal Range	Units
Pulse Rate	50 – 100	beats per minute (bpm)
Systolic Blood Pressure	90 - 140	mm Hg
Diastolic Blood Pressure	40 - 90	mm Hg
Respiratory Rate	10 - 22	respirations per minute
Oral Temperature	35.5 – 37.5	°C
Pulse Oximetry	≥ 95	%

ECG PARAMETERS

Parameter	Normal Range	Units
Heart Rate	50 – 100	bpm
PR Interval	≥ 120 to ≤ 220	msec
QRS Duration	< 120	msec
QT Interval	< 500	msec
QTcB	≤ 450 (both genders)	msec
QTcF	≤ 450 (both genders)	msec

Appendix 5 List of Laboratory Tests

Hematology:
 
 Hematocrit (Hct) Hemoglobin (Hgb) Mean corpuscular volume (MCV) Platelet count Red blood cell (RBC) count White blood cell (WBC) count with differential 
Urinalysis:
 
 Bilirubin Glucose Ketones Leukocytes Nitrite Blood pH Protein Specific gravity Urobilinogen 
If there are any abnormalities considered clinically significant, the urine sample will be sent for microscopic examination.
 
Serology:
 
 HBsAg, HCV, and HIV 	
Serum Chemistry:
 
 Albumin (ALB) Alkaline phosphatase (ALP) Alanine aminotransferase (ALT; SGPT) Aspartate aminotransferase (AST; SGOT) Bicarbonate Blood urea nitrogen (BUN) Calcium (Ca) Chloride (Cl) Creatinine Gamma-glutamyl transferase (GGT) Glucose Lactate dehydrogenase (LDH) Phosphate Potassium (K) Sodium (Na) Thyroid stimulating hormone (TSH) Free triiodothyronine (T3) Free thyroxine (T4) Total bilirubin Total protein 
Coagulation:
 
 Prothrombin time (PT) Activated partial thromboplastin time (PTT)
--	--

Serum human chorionic gonadotropin (hCG) (only for females who are not diagnosed as postmenopausal)
 
Urine pregnancy test
	
Urine Drug Screen for benzodiazepines, cannabinoids, methadone, opiates, sympathomimetic amines, and cocaine.
 
Panel Drug Screen for Amphetamines (AMP) Methamphetamines (MET), Methadone (MTD), Barbiturates (BAR), Benzodiazepines (BZO), Cocaine (COC), Opiates (OPI), 3,4-Methylenedioxyamphetamine (MDMA), Phencyclidine (PCP), Tetrahydrocannabinol (THC)

--	--

Normal reference ranges will be included in the Study Procedures Manual and /or Laboratory Manual.

Appendix 6 Country-Specific Safety Reporting (Australia)

For clinical sites in Australia, the following local requirements apply, in addition to safety reporting requirements discussed in the main protocol.

Significant Safety Issue

In Australia, an SSI is defined as “a safety event that could adversely affect the safety of subjects or materially impact on the continued ethical acceptability or conduct of the trial” (Reference: NHMRC [2016] Guidance: Safety monitoring and reporting in clinical trials involving therapeutic goods).

Kinoxis is responsible for reporting to the Australian Therapeutic Goods Administration (TGA) in a timely fashion for any SSIs that occur at any site on the study worldwide.

Urgent Safety Measure

In Australia, USMs are one type of SSI where Sponsors or trial investigators act immediately to protect participants from an immediate hazard to their health and safety.” (Reference: NHMRC (2016). Guidance: Safety monitoring and reporting in clinical trials involving therapeutic goods)

Kinoxis is responsible for reporting to the Australian TGA and the HREC (Human Research Ethics Committee) within 24 hours of learning of any USMs that occur at any site on the study worldwide.

1 INTRODUCTION

The statistical analysis plan (SAP) details the planned statistical analysis methods required to address the study objectives as described in Kinosis Therapeutics Pty Ltd's (Kinosis) protocol KTX-101: A Phase 1 Study Investigating the Safety, Tolerability and Pharmacokinetics of KNX100 in Healthy Volunteers.

This SAP should be read in conjunction with the study protocol, case report form (CRF), and any other applicable study documents. This version of the SAP is based on the protocol version 6.0, dated 07 July 2023. Changes to the protocol may result in subsequent changes to the SAP. The final, sponsor-approved version of the SAP must occur prior to database lock.

2 STUDY OBJECTIVES AND ENDPOINTS

Objectives	Endpoints
Primary	

The primary objectives of this study are to evaluate the safety and tolerability of KNX100 administered orally as a single ascending dose and multiple ascending doses in healthy volunteers.	
Incidence of treatment-emergent adverse events (TEAEs) and treatment-emergent serious adverse events (TESAEs), related AEs, AEs leading to discontinuation, and AEs by severityClinical laboratory testing from protocol-specified standard urine and blood tests, including liver function tests (LFTs) and thyroid function tests (TFTs: triiodothyronine [T3], thyroxine [T4], thyroid stimulating hormone [TSH])Change in clinical observations from baseline, including body temperatures, vital signs, electrocardiograms (ECGs), electroencephalograms (EEGs)
Secondary	

To determine the pharmacokinetic (PK) profile of KNX100 and its metabolites following administration of KNX100 as single and multiple oral doses administered once and twice daily in healthy volunteers.	
Maximum observed concentrations (C_{max}) following dose administrationTime of C_{max} (T_{max}) following dose administrationArea under the concentration-time curve (AUC) from time zero to last quantifiable concentration (AUC_{0-last}), from time zero to 24 hours post-dose administration (AUC_{0-24}), and, as data permit, from time zero to extrapolated to infinity ($AUC_{0-\infty}$)

	
• As data permit, additional disposition parameters including terminal half-life ($t_{1/2}$), volume of distribution (V_z/F), and oral clearance (CL/F) may be calculated• Accumulation Ratio (RAC) for C_{max} and AUC_{0-24}; Day 7 vs Day 1 (MAD phase only)• Other PK parameters will be calculated as deemed appropriate and as referred to in Section 8.7 of the protocol
--	--

3 STUDY DESIGN

3.1 General Description

This is a Phase 1, first-in-human (FIH), single site, single treatment, two-part, double-blind, placebo-controlled, randomized, single ascending dose (SAD)/multiple ascending dose (MAD) study. The planned enrollment is approximately 64 male and female subjects. The total number of subjects will depend on the number of dose levels assessed in dose-escalation. Completed subjects will have received either KNX100 (active study drug) or placebo. Subjects who discontinue will be replaced to achieve the targeted number of evaluable subjects in each cohort.

[figure not shown]
Healthy subjects who meet all eligibility criteria will be sequentially enrolled and assigned to a single cohort in Cohorts 1-4 in Part A (SAD) of the study or in Cohorts 1-3 in Part B of the study. Each cohort selected will evaluate 8 subjects who will be randomly assigned with a ratio of 6:2 to receive either KNX100 or placebo. Each cohort will be enrolled sequentially, and the subsequent dose increase will be based on the Cohort Review Committee (CRC) evaluation of data known to date. Additional cohorts may be added as required, based on safety profile and CRC authorization.

Part A (SAD) will initially dose two sentinel subjects (one assigned to KNX100 and one assigned to placebo) in Cohort 1. The center will review safety and tolerability up to and including the 48-hour timepoint for the sentinel subjects before dosing the remaining subjects in the dose cohort. The CRC will be informed and authorize the decision to continue with the remainder of the cohort dosing. Each subject will receive one dose, administered orally, of study drug. All subjects in each cohort will have their data, up to and including the 30-hour post-dose timepoint, evaluated for safety and tolerability by the CRC before opening the next dose cohort based on assessment of all available data. The dosing schedule may be extended if additional observations are needed at a particular cohort. In the absence of unacceptable AEs, the CRC may decide to open the next cohort before they have reviewed all data from all 8 evaluable subjects who have completed up to and including the 30-hour post-dose timepoint. Subjects will be housed in the clinic from Day -3 prior to study drug administration and will remain in-house for 30 hours post-dose (Day 2) for PK and safety assessments.

Part B (MAD) will evaluate up to 3 doses based on the doses established during Part A (SAD). Each subject in Cohorts 1 and 2 will receive study drug for 7 days, administered once daily. Subjects in Cohort 3 will receive study drug for 7 days, administered twice daily. All subjects in each Part B (MAD) cohort will have their AE, PK, and electroencephalography (EEG) data, acquired up to and including Day 8, evaluated for safety and tolerability by the CRC before opening the next higher dose cohort. Subjects will be housed in the clinic from Day -3 prior to study drug administration and will remain in-house for 24 hours post morning dose (Day 8) for PK and safety assessments.

The study will be comprised of 3 periods: Screening (up to 28 days); Treatment (1 day for Part A (SAD) subjects and 7 days for Part B (MAD) subjects); and Follow-up. Subjects will have a follow-up visit 7 days after the last dose. As SAD dosing is a single dose on Day 1, follow-up will occur on Day 7. Part B (MAD) Cohorts 1 and 2 dosing involves single daily dosing on Days 1 to 7, with a follow-up visit occurring on Day 14. Part B (MAD) Cohort 3 dosing involves twice daily dosing on Days 1 to 7, with a follow-up visit occurring on Day 14.

Figure 1. Study Phases and Activities

3.2 Randomization and Blinding

Subjects will be centrally randomized to treatment in a 6:2 ratio within each assigned cohort. The first 2 sentinel subjects will be assigned to treatment in a 1:1 ratio such that 1 subject receives KNX100 and the other receives placebo. Once eligibility is re-confirmed (Day -1), subjects will be randomized via a randomization list.

The study will be performed in a double-blind fashion. The investigator and study staff (including lab personnel), the subjects, the monitors, and the Sponsor's staff will remain blinded to treatment assignment until database lock. The investigator will receive sealed envelopes with the individual randomization per subject to be opened in the case of emergency only. To ensure study blinding, the active and placebo will be provided in identical capsules and an equivalent number of capsules will be administered to subjects receiving placebo.

The site pharmacy staff will be unblinded. Additionally, the following roles may be unblinded: Unblinded biostatistics team that prepares the randomization materials and handles treatment-revealing data prior to database lock; selected study Sponsor personnel who are not directly involved in the conduct of the study; and the drug-reconciliation clinical research associate (CRA). A list of unblinded individuals will be maintained in study files.

Subjects may be unblinded in the event that an AE of Grade 3 or greater is reported in 2 or more subjects to support CRC data review and decisions regarding dose escalation or stopping criteria. If deemed necessary, the CRC may be required to break the randomization code.

3.3 Sample Size

The sample size for this study is planned for approximately 64 subjects. The sample size for this study has been selected without performing a formal sample size calculation.

3.4 Cohort Review Committee

An independent CRC will oversee the progress of the study and periodically review the accruing safety data. The CRC is intended to ensure that treatment does not pose undue risk to subjects. The CRC will include an appropriate group of professional specialties, including at a minimum, the following: blinded primary investigator (PI) or delegate (must be a physician), blinded medical monitor or delegate (must be a physician), blinded neurologist with expertise in EEG analysis and interpretation, and a blinded pharmacokineticist.

For Part A (SAD), the CRC will review all safety and PK data of the sentinel subjects, collected up to the 30-hour post-dose timepoint, to enable the decision to enroll the rest of the cohort. Any AE in a sentinel subject assessed as related to study medication may trigger the need for a safety evaluation by the CRC to determine if additional subjects in the cohort may be dosed. The CRC will also conduct a blinded, cohort-escalation review after the final subject in a cohort has been dosed, using safety data from all subjects through at least the 30-hour post-dose timepoint, as well as all available blinded PK and safety data from the current and previous cohorts.

For Part B (MAD), the CRC will review all safety and PK data from each cohort collected up to and including the 24-hour post-dose timepoint on Day 8. Additionally, the frequency and severity of the following events and findings will be used to determine the acceptability of escalation to the next cohort:

- Serious AEs
- AEs leading to study discontinuation
- AEs
- Clinically significant laboratory, EEG, and ECG findings
- Study medication sensitivities and reactions

3.5 Interim Analysis

There is no formal interim analysis planned for this study. Ongoing cohort reviews will be performed for dose escalation decisions as described in section 3.4.

The final analysis will occur once all subjects complete their end of study (EOS) visit or discontinue from the study.

4 ANALYSIS SETS/POPULATIONS

4.1 Safety Set

The Safety Set (SAF) will include all subjects who received at least one dose of study treatment. Subjects will be analyzed according to the treatment received. The SAF will be used for all safety summaries.

4.2 Per Protocol Set

The Per Protocol Set (PP) will include all subjects who received at least one dose of any amount of KNX100 and do not have major protocol violations as defined in Section 9.9 of the protocol. A final determination of inclusion in the PP will be made by a blinded team prior to database lock and unblinding. The PP may be used on select biomarker endpoints. Subjects will be analyzed according to the randomized treatment assignment.

4.3 Pharmacokinetic Set

The Pharmacokinetic (PK) Set will include all subjects who received at least one dose of any amount of KNX100 and had sufficient plasma KNX100 concentration data for calculation of at least one PK parameter (among AUC₀₋₂₄, C_{max} or T_{max}).

Subjects with protocol violations will be assessed on a participant-by-participant basis for inclusion in the PK Population.

5 GENERAL CONSIDERATIONS

5.1 General Data Handling

All safety analyses will be conducted based on SAS 9.4 or higher.

Placebo subjects will be pooled across cohorts.

Data in the clinical database as well as vendor data will be presented in by-subject data listings.

Continuous data will be summarized by study part and cohort based on n, mean, median, standard deviation (SD), first quartile (Q1), third quartile (Q3), minimum value, and maximum value.

Categorical data will be summarized by study part and cohort using frequency counts and percentages. Unless otherwise stated, the denominator of percentages will be the number of participants in the population/cohort or the number with non-missing data.

- In summaries pertaining to subject demographics and subject disposition, the number of missing values will be presented as a separate category with no percentage, but only if one or more subjects are missing data.
- Counts of zero will be presented without percentages.

No inferential statistics will be produced for any safety endpoints.

Relative to the number of digits after the decimal in the raw data, summary statistics will have the following number of digits after the decimal:

- Minimum and Maximum: same number of significant digits as the raw data
- Mean, Median, Q1, and Q3: one additional significant digit
- SD: two additional significant digits
- Percentages <100% will be reported to one decimal place and percentages of 100% will be reported with no decimal place. The number and percentage will be presented in the form of XX (XX.X%). Percentage values of less than 0.1% will be presented as XX (<0.1%).
- Summary statistics will not exceed four digits after the decimal. Some laboratory parameters or other data may require deviation from this rule.

For clinical laboratory data, results reported as below the lower limit of quantification (LLOQ) or above the upper limit of quantification (ULOQ) will be replaced by the LLOQ and ULOQ, respectively, to ensure inclusion in applicable tables and figures, but will be presented in applicable listings as originally reported.

All data up to the time of study completion/withdrawal from the study will be included in the analysis, regardless of duration of treatment.

Numbering for data displays will be based on International Council for Harmonization (ICH) E3.

5.2 General Definitions

Variable	Definition
Study Day	
 • Study Day = date of interest – treatment start date + 1, when the date of interest \geq treatment start date; • otherwise, Study Day = date of interest – treatment start date. 
Note: if either date is missing, Study Day calculations will not be performed. Should imputation be performed, then Study Day may be computed, where appropriate.

Baseline	
For ECG data, baseline is defined as the average of up to three measurements taken at the pre-dose timepoint on the Day 1 Visit if available; otherwise, baseline is defined as the last single tracing measurement taken prior to the first dose of study treatment.
 
For EEG data, baseline is defined as the assessment collected at the Screening Visit (Day -2) in which the patient was in a sleep deprived state.
 
For all other endpoints, baseline is defined as the last non-missing value collected prior to receiving the first dose of study treatment (based on date and time of administration as applicable). For endpoints with both planned pre-dose and post-dose timepoint assessments on Day 1, only pre-dose assessments will be considered as a candidate for baseline. For MAD Cohort 3, vital signs

	assessments on Day 1 associated with the second dose (i.e., evening) will not be considered as a candidate for baseline.
Post-baseline	Defined as values collected after receipt of the first dose of study treatment (based on date and time of administration as applicable)
Change from Baseline	Defined as: Post-baseline value – Baseline value
Duration on Study (in days)	End of study date – randomization date + 1
BMI (kg/m ²)	BMI is collected in the clinical database
Age (yr)	Age is collected in the clinical database
Study Completion	Defined as attendance at the End of Study (EOS) Visit.

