- Nonhormonal intrauterine device (IUD)
- Bilateral tubal occlusion
- Vasectomized subject/partner with documented azoospermia 90 days after procedure if that partner is the sole sexual partner.

For female participants, hormonal contraceptives should begin at least 1 month prior to screening to ensure contraceptive is in full effect.

Complete abstinence, defined as the complete avoidance of heterosexual intercourse, is an acceptable form of contraception if used consistently throughout the duration of study and for the durations after dosing specified for males and females above. It is not necessary to use any other method of contraception when complete abstinence is elected. WOCBP who choose complete abstinence must continue to have pregnancy tests as per protocol. The reliability of sexual abstinence needs to be evaluated by the investigator in relation to the duration of the clinical study and the preferred and usual lifestyle of the subject.

6.10. 12-Lead Electrocardiograms

12-lead ECGs will be used to evaluate heart rate, atrial ventricular conduction, QRS and QT intervals, and possible arrhythmias. ECGs include ventricular heart rate; QRS duration; PR, RR, QT, QTcB, and QTcF intervals; and P and T wave. Evaluations will be recorded as normal, abnormal (not clinically significant), or abnormal (clinically significant).

The 12-lead ECGs will be obtained after the subject has been resting semi-supine for at least 3 minutes prior to the indicated times. All ECGs should be recorded with the subject in the same physical position. For each time point, 3 ECG recordings should be taken at approximately 1 to 3-minute intervals.

A standardized ECG machine should be used, and the subject should be tested using the same machine throughout the study, if possible. When the timing of these measurements coincides

with a blood collection, obtain the ECG prior to the nominal time of the blood collection, blood pressure, and heart rate.

Additional ECGs should also be collected if a subject experiences a cardiac AE.

After ECGs have been recorded, the PI or a designated physician will review each of the ECGs. If available, a paper copy should be filed in the subject's medical records. For all ECGs, ECG intervals and an overall assessment will be recorded. Evaluations will be recorded as normal, abnormal (not clinically significant), or abnormal (clinically significant).

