⁶ Vital signs collection includes systolic and diastolic blood pressures, pulse rate and body temperature which will be measured with the subject to be seated or semi-supine after resting for at least 3 minutes. Vital signs also include respiratory rate, continuous pulse oximetry and saturated oxygen, which will be undertaken via telemetry within 2 hours predose and at 30 hours (\pm 30 minutes) after dosing. Measurements of all vital signs will be recorded within 1 hour predose, and at 30 minutes, 1-, 1.5-, 2-, 4-, 6-, 8-, 12-, 24- and 30-hours postdose (\pm 15 minutes). Peak flow measurement will also be undertaken within 1 hour predose as well as at 1-, 2-, and 4-hours (\pm 15 minutes) postdose. The highest of 3 peak flow measurements, at each timepoint, shall be recorded.

⁷ Subjects should fast overnight prior to collection of laboratory tests at Screening. The Day 1 laboratory tests will be undertaken at 1 hour postdose (\pm 15 minutes) and at 24 hours (\pm 15 minutes) postdose (Day 2).

⁸ The Day 1 urinalysis tests will be undertaken at 1-hour postdose (\pm 60 minutes) and at 24 hours (Day 2) (\pm 60 minutes) postdose.

⁹ Serum pregnancy test at Screening and End of study visit. A urine pregnancy test will be conducted in women of child-bearing potential on admission to unit on Day -3.

¹⁰ Test may be repeated if required.

¹¹ Each subject will receive study drug based on randomization (placebo or KNX100), after a 10 hour fast.

¹² Please refer to [Appendix 3](#) for information related to PK assessments and sampling times.

¹³ Plasma samples for biomarker analyses will be collected predose (Day -1), on Day 1 at 1-hour postdose (\pm 15 minutes), and at EOS/EOT.

¹⁴ EEG: Please refer to [Appendix 3](#) for information related to EEG assessments.

¹⁵ Please refer to [Appendix 3](#) for information related to ECG assessments which will be performed in triplicate. The timing and number of ECGs may be altered, depending on the emerging PK and safety profile. Additional ECGs should also be collected if a subject experiences a cardiac adverse event.

¹⁶ Participants will be admitted to the Phase 1 unit on Day -3 so they can sleep for 4 hours prior to undertaking their sleep deprived EEG on Day -2, through to 30 hour testing on Day 2.

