¹⁴ Please refer to [Appendix 3](#) for information related to ECG assessments. ECGs will be undertaken in triplicate. The timing and number of ECGs may be altered, depending on the emerging PK and safety profile. ECGs should also be collected if a subject experiences a cardiac adverse event.

¹⁵ EEG: Please refer to [Appendix 3](#) for information related to EEG assessments.

¹⁶ C-SSRS: will be administered predose at screening and then within 4 hours post the morning dose on Days 4 and 7.

¹⁷ Subjects will be admitted to the unit on Day -3 to undertake their sleep deprived EEG. Subjects will remain in the unit during the entire dosing phase and be discharged after collection of Day 8 assessments.

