Appendix 3 PK Blood Sampling, EEG and ECG Schedule During Dosing Periods

Time Relative to Dose	Part A (SAD, HV)						Part B (MAD, HV)					
	Day 1			Day 2 ¹			Day 1-7					
							Cohorts 1-2			Cohort 3		
	PK ²	ECG ³	EEG ⁴	PK ²	ECG ³	EEG ⁴	PK ²	ECG ³	EEG ⁴	PK ⁵	ECG ³	EEG ⁴
Predose	X	X	X	X		X	X	X	X	X	X	X
15 minutes	X					X						
30 minutes	X					X		X	X			X
1 hour	X	X				X	X		X	X		
2 hours	X	X				X			X			
4 hours	X	X				X			X			
8 hours	X	X				X			X			
8.5 hours									X			
9 hours									X			
10 hours									X			
12 hours	X					X			X			
16 hours	X	X							X			
24 hours		X	X	X		X			X			X
30 hours				X								

Abbreviations: ECG = electrocardiogram; EEG = electroencephalography; HV = healthy volunteer; MAD = multiple ascending dose; PK = pharmacokinetics; SAD = single ascending dose.

¹ For Part A (SAD), Day 2 is the 24-hour timepoint after last study drug administration. For Part B (MAD), Day 8 is the 24-hour timepoint after last study drug administration (Cohorts 1 and 2) and 24-hours post morning dose (Cohort 3). This visit will be used to collect only the “24-hour” samples.

² During Part A (SAD), PK samples and time windows are predose, and 15 minutes (± 2 minutes), 30 minutes (± 2 minutes), 1 hour (± 5 minutes), 2-, 4-, 8-, 12-, and 24- and 30-hours (± 30 minutes) postdose. During Part B (MAD Cohorts 1 and 2), PK samples will be taken at predose and 15 minutes (± 2 minutes), 30 minutes (± 2 minutes), 1-hour (± 5 minutes), 2-, 4-, 8-, and 12- hours (± 15 minutes) postdose on Days 1, 4 and 7. The timing and number of PK samples may be altered depending on emerging data and safety profile.

³ Part A (SAD) ECGs and time windows are Screening, Day -1, predose, 1 hour (± 2 minutes), 2-, 4-, 8-, and 16-hours (± 5 minutes), and 24-hours (± 30 minutes). For the MAD part of the study, ECGs will be undertaken at Screening, Day -1, predose, and 1-hour postdose (± 30 minutes) on Day 1 to Day 7. ECGs will be measured with the subject to be seated or semi-supine after resting for at least 3 minutes.

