6.4.5 Electrocardiogram (ECG)

Electrocardiogram (ECG) parameters include: HR (beats/min), PR interval (msec), RR interval (msec), QRS duration (msec), QT interval (msec), QTcB interval (msec), QTcF interval (msec), P wave (msec), and T wave (msec). Observed values and changes from baseline for ECG parameters

will be summarized by study part and cohort at each visit and time point. If triplicate reads are taken, the mean of the reads will serve as the observed value at the specific visit and timepoint.

Investigator-reported ECG findings shifts from baseline to each post-baseline visit/timepoint and maximum post-baseline will be summarized by study part and cohort. Categories of Normal, Abnormal – Not Clinically Significant, and Abnormal – Clinically Significant will be included.

Subjects meeting the following potentially clinically significant criteria post-baseline will also be presented:

- 450 msec < QTcF / QTcB ≤ 480 msec
- 480 msec < QTcF / QTcB ≤ 500 msec
- 500 msec < QTcF / QTcB
- 30 msec < QTcF / QTcB change from baseline ≤ 60 msec
- 60 msec < QTcF / QTcB change from baseline

All ECG parameter results will be provided in by-subject data listings.

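### When no Day 1 pre-dose ECG exists, SAP 5.2 takes a single tracing as baseline rather than the mean of the last triplicate, adding avoidable noise to QTc change in what should be rare cases

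*SAP*

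**What the plan says.** **Main rule (SAP Section 5.2).** "For ECG data, baseline is defined as the average of up to three measurements taken at the pre-dose timepoint on the Day 1 Visit if" such measurements exist. The words on up to three measurements mean that one or two Day 1 tracings are enough to stay under this rule.

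**Fallback (same section).** "otherwise, baseline is defined as the last single tracing measurement taken prior to the first dose of study treatment".

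**Collection plan (Protocol).** Section 6.10: "For each time point, 3 ECG recordings should be taken at approximately 1 to 3-minute intervals". The schedule footnotes agree: Appendix 1 refers to "ECG assessments which will be performed in triplicate", and Appendix 2 says "ECGs will be undertaken in triplicate". Appendix 3, footnote 3, places ECGs before Day 1 in both parts. For Part A, "Part A (SAD) ECGs and time windows are Screening, Day -1, predose" and then the post-dose times; for Part B, "ECGs will be undertaken at Screening, Day -1, predose, and 1-hour postdose".

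**Observed value (SAP Section 6.4.5).** "If triplicate reads are taken, the mean of the reads will serve as the observed value" at that visit and timepoint.

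**Use of baseline.** SAP Section 5.2 defines change as the post-baseline value minus baseline. SAP Section 6.4.5 summarises ECG change by cohort and timepoint. It also presents subjects whose QTcF or QTcB rises by more than 30 and up to 60 ms, or by more than 60 ms.

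**The concern.** If a subject has no Day 1 pre-dose tracing, the last earlier ECG is normally the Day -1 triplicate. SAP 6.4.5 would report the mean of those three tracings as the Day -1 value. SAP 5.2 would take only the last of the same three as baseline. Change from baseline then sets a post-dose mean of three against one reading, and two usable recordings are left out. The SAP gives no reason for the difference.

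ECG change from baseline is among the primary safety endpoints (Protocol Section 8.5.1). The change categories above 30 and 60 ms depend directly on the baseline value. With six active subjects per cohort, one spurious flag moves a cohort from 0% to 1/6 = 16.7%.

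**Working it through.** The documents give no QTc standard deviation and no figure on this point, so there is nothing of the plan's own to reproduce.

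**Inputs from the documents**
- Post-dose value: mean of 3 tracings (Protocol 6.10, SAP 6.4.5).
- Baseline tracings *m*: 1 under the fallback, 3 if the last pre-dose triplicate is averaged.

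**Assumed inputs**
- Replicate SD *s_r* (tracings minutes apart): 4 to 12 ms.
- Between-occasion SD *s_o* (different times or days): 5 to 10 ms, with 0 as a limiting case.
- Normal errors and no true change.

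**Formula**

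Var(change) = 2·s_o² + s_r²·(1/3 + 1/m)

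**Replicate part alone**
- m = 1: s_r²·(1/3 + 1) = 4/3·s_r²
- m = 3: s_r²·(1/3 + 1/3) = 2/3·s_r²
- The ratio is 2 whatever s_r is. Baseline replicate variance itself is s_r² against s_r²/3, a ratio of 3.

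**Two worked cases**
- s_r = 8, s_o = 8. Single: √(128 + 85.3) = 14.6 ms. Triplicate: √(128 + 42.7) = 13.1 ms.
- s_r = 10, s_o = 5. Single: √(50 + 133.3) = 13.5 ms. Triplicate: √(50 + 66.7) = 10.8 ms.

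The chance of a spurious increase above 30 ms at one timepoint is 1 − Φ(30/SD):

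| s_r, s_o (ms) | SD single | SD triplicate | SD ratio | P(>30 ms) single | P(>30 ms) triplicate |
|---|---|---|---|---|---|
| 4, 10 | 14.9 | 14.5 | 1.03 | 2.2% | 1.9% |
| 8, 8 | 14.6 | 13.1 | 1.12 | 2.0% | 1.1% |
| 10, 5 | 13.5 | 10.8 | 1.25 | 1.3% | 0.3% |
| 12, 5 | 15.6 | 12.1 | 1.29 | 2.7% | 0.7% |
| 12, 10 | 19.8 | 17.2 | 1.15 | 6.5% | 4.1% |

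The first and fourth rows are the ends of the SD ratio over the assumed range. The last row has the largest flag probabilities.

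**Several timepoints sharing one baseline.** Part A has six post-dose ECGs in the dosing period (1, 2, 4, 8, 16 and 24 hours). In a simulation at s_r = 8 and s_o = 8, with independent post-dose occasions, at least one spurious increase above 30 ms occurs in 7.6% of subjects with a single-tracing baseline and 4.9% with a triplicate baseline.

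**The case against.** **The fallback should almost never be used.** It needs all Day 1 pre-dose tracings to be missing, since a partial set stays under the main rule. Subjects are in the unit from Day -3. Exclusion criterion 5 (Protocol Section 4.3) names the pre-dose Day 1 ECG, so a subject dosed without it would have an incomplete eligibility check. This stands. The documents give no rate of missing ECGs, and the number affected may be zero.

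**A reader might infer that SAP 5.2 flatly contradicts SAP 6.4.5.** The documents do not go that far. The averaging rule in 6.4.5 is conditional on triplicates having been taken, and it defines the value at a visit; 5.2 is the specific rule for baseline. SAP Section 5.4 allows unscheduled data into baseline summaries, and a lone unscheduled tracing could be the last pre-dose ECG. It also makes the later of several values the general default. Triplicates are planned rather than guaranteed: Appendices 1 and 2 allow the timing and number of ECGs to change. The two rules are misaligned for a Day -1 triplicate. But 5.2 does not limit the fallback to cases with only one tracing, so a programmer following it literally would drop two of three.

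**A reader might also quote a 41% larger SD of change.** That figure, and a false-flag contrast of 0.47% against 0.012% at a replicate SD of 10 ms, follow only if between-occasion variation is zero. Baseline and post-dose ECGs are taken at different times, and under the fallback normally on different days, so zero is not a sensible working value. With 5-10 ms of such variation the contrast is about 2-fold and 5-fold in the 8 and 8 ms and the 10 and 5 ms cases.

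**The consequence is limited.** No inferential statistics are planned for safety, all ECG results are listed by subject, and the absolute QTc categories do not use baseline. The added error is random, not a bias in one direction. All of this stands, and it keeps the point minor.

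**Conclusion.** The point holds as a minor, optional improvement. No other text in the SAP or protocol corrects the fallback.

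For an affected subject, the doubling of the replicate part of the variance needs only post-dose triplicates, an available pre-dose triplicate and independent replicate errors. The effect on total SD, 1.03 to 1.29 times, and the flag probabilities rest on the assumed SD ranges and on normality. Averaging the Day -1 triplicate would not remove day-to-day variation; it removes only the avoidable part of the noise. No error rate or study conclusion is at risk.

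**What to change.** In SAP Section 5.2, replace the ECG fallback with: *otherwise, the mean of all available replicate tracings at the last timepoint before the first dose of study treatment; a single tracing is used only if just one exists.*

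This brings the baseline into line with Section 6.4.5 and still covers a lone unscheduled tracing. It costs one phrase in the SAP and the matching line of programming, best made before database lock. It needs no extra data, because the replicates are already planned, and it has no evident downside.
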